4.3. Pharmacy Procedures

Once a participant is determined to be eligible and enrolled into the study, study participants will go to Health Park Pharmacy, Raleigh, NC, to receive methadone administration and take-home methadone doses for Opioid Use Disorder from the study pharmacist(s) for approximately 3 months. Participants will receive their take-home methadone doses from the pharmacy on a once-a-week or every 2-week schedule, consistent with their methadone take-home schedule at the study OTP program (Morse Clinic of North Raleigh, NC; Morse Clinic of Zebulon, NC). The prescriptions will be written by the site PI (Morse Clinic of North Raleigh, NC; Morse Clinic of Zebulon, NC), [name], DFAPA, who will have been granted an exception by the DEA to write prescriptions for methadone for the treatment of Opioid Use Disorder. Each prescription will include the OTP's registration number, in addition to the prescriber's DEA number, and indication for Opioid Use Disorder. Prior to dispensing take-home doses to a participant at each pharmacy visit, the study pharmacist will observe ingestion of one dose at each visit. All methadone dispensed by the pharmacy for this study will be from the pharmacy's stock supply. The costs of methadone medication dispensed at the pharmacy for the study will be paid by research funds from the National Institute on Drug Abuse, the National Institutes of Health (NIH).

Participants will complete three follow-up assessments at 1-month, 2-months, and 3-months following the baseline visit. These follow-up assessments will be completed either in-person between the participant and research staff or remotely via phone or a Duke-approved teleconferencing platform for research. Assessments will focus on collecting clinical and safety information since the previous assessment, including substance use data via urine toxicology samples and self-report using the timeline followback (TLFB) assessment, compliance with psychosocial interventions, medication side effects or other safety events, and suicidality risk evaluation. The full list of assessments to be administered is included below (**Table 1**). Based on the convenience of the patient's time and methadone take-home schedule, monthly research assessment may be scheduled to occur on a day that take-home doses are scheduled to be dispensed. Completion of the intake/baseline assessments will take approximately 45-60 minutes. Follow-up research interviews will be briefer, about 30 minutes in duration.

Using the guidance from the pharmacy practice's collaborative practice agreements (CPAs), the role and responsibilities of study pharmacists (Health Park Pharmacy, Raleigh, NC) and study OTP prescriber/physician ([name]), including communication procedures, will be specified by an Operational Care Agreement (OCA) and signed by study pharmacists and [name]. Throughout the study, participants will continue to receive their usual care at the OTP (e.g., counseling, methadone provider

oversight of dose orders, urine drug screen) and participants will return to their OTP at the end of the study (i.e., 3 months after baseline). The last monthly study assessment (3 months after baseline) will occur remotely (via phone or a Duke-approved teleconferencing platform), at the OTP, or at the pharmacy; however, no methadone will be dispensed at the pharmacy as part of the 3-month assessment.

4.4. Assessments

Study assessments will focus on the feasibility (e.g., recruitment, implementation of the intervention), treatment adherences, and safety measures. A list of assessments by the study visit is summarized in **Table 1**. Assessments are categorized as either general and medical assessments, safety assessments, substance use assessments, or methadone treatment and satisfaction assessments. A detailed description of each assessment is provided following the study assessment timetable.

Table 1: Study Assessment Timetable

Study visit number	Visit 1	Visit 2*_	Visit 3	Visit 4	Visit 5	Early termination	
Visit location**	OTP/remote	Pharmacy	OTP, Pharmacy, remote	OTP, Pharmacy, remote	OTP, Pharmacy, remote	OTP, Pharmacy, remote	
Assessment/Activity	Screening/ Baseline	Methadone dosing and dispensing	1 Month After Visit 2	2 Months After Visit 2	3 Months After Visit 2		As needed
General and Medical Assessments							
Recruitment Log	x						
Prisoner Status Assessment	x		x	x	x		x
Informed Consent/HIPAA/ Medical Release Form	x						x
Master Enrollment Log	x						
Inclusion/Exclusion Checklist +	x						
Locator Form	x		x	x	x		x
Demographics	x						
Medical History	x						
Substance use history	x						
Charlson Comorbidity Index	x						
Concomitant Medications	x		x	x	x		x
Study Completion					x	x	
Protocol Deviations							x
Missed Visit							x
Safety Assessments							
Patient Health Questionnaire (PHQ-9)	x		x	x	x	x	
P4 suicide screener (P4 screener) (Follow-up assessment will be triggered by the PHQ-9 result) ++	x		see ++	see ++	see ++		x
Safety Event Response Checklist	x		x	x	x		x
Pregnancy and birth control assessment	x		x	x	x		x
Substance Use Assessments							
Urine Drug Screen (UDS) (the OTP records)	x		x	x	x		x
Timeline Followback (TLFB)	x		x	x	x	x	
Methadone Treatment and Satisfaction Assessments							
Methadone Call Back (once)			see +++	see +++	see +++		x+++

Study visit number	Visit 1	Visit 2*_	Visit 3	Visit 4	Visit 5	Early termination	
Visit location**	OTP/remote	Pharmacy	OTP, Pharmacy, remote	OTP, Pharmacy, remote	OTP, Pharmacy, remote	OTP, Pharmacy, remote	
Assessment/Activity	Screening/Baseline	Methadone dosing and dispensing	1 Month After Visit 2	2 Months After Visit 2	3 Months After Visit 2		As needed
(the OTP records)+++							
OTP's Psychosocial Counseling Attendance Form (the OTP records)	x		x	x	x	x	
Methadone Visit Checklist++++		x	x	x	x		x
End of Methadone Medication Form					x	x	
Treatment Satisfaction Survey	x		x	x	x	x	

* Visit 2 refers to the pharmacy visit for the **first** methadone dose administration. The timing of the subsequent follow-up visits are anchored at visit 2.

** Remote pre-screening and screening, remote consenting (eConsent), and remote data collection (study assessments) by phone or the Duke-approved teleconferencing platform for research also will be used.

+ Inclusion/exclusion criteria: Medical record data at the OTP will be used to determine study eligibility status.

++ P4 Screener: Follow-up assessment for suicide risk by P4 Screener will be triggered by the PHQ-9 result. Endorsements of suicidality on the PHQ-9 (i.e., if the participant answers Q9 "Thoughts that you would be better off dead, or of hurting yourself in some way" as "Several days", "More than half the days" or "Nearly every day") will trigger the completion of the P4 Screener form. A positive finding will be reported promptly to Site PI for further medical evaluation and clinical decision.

+++ Methadone Call Back: At least one random methadone call-back visit will occur during the study period (i.e., after the first methadone dispensing at the pharmacy).

++++ Methadone Visit Checklist: Methadone for Opioid Use Disorder will be administered and dispensed by study pharmacist(s) at Visit 2 (after enrollment into the study) and subsequently according to the length of time prescribed by the OTP physician for a total of 3 months. This form will be completed by the study pharmacist at each pharmacy visit. The number of pharmacy visits will be based on each participant's methadone take-home doses and treatment schedule.

4.4.1. General and Medical Assessments (Note: The visit numbers used in this section follow the order indicated in the Study Assessment Timetable.)

Recruitment Log: Drawing on the information captured in the Master Enrollment Log, as well as by reviewing the signed consent forms, the Recruitment Log will collect data on the number of potential participants who have been pre-screened for participation in the study and the number of participants who signed the informed consent form. These data will be used monthly to calculate the recruitment rates during the month enrollment phase. Data from this log will be used to project the number of participants and inform the duration of enrollment (i.e., recruitment rate) for a future multi-site clinical trial.

Prisoner Status Assessment: The Prisoner Status Assessment will be administered at the intake/baseline visit (Visit 1) and at the beginning of each monthly study visit to determine whether a participant is incarcerated/detained in a correctional facility, pending trial, or otherwise meets the definition of a prisoner as delineated in 45 CFR 46.303(c) as adopted by the Office for Human Research Protections (OHRP). Prisoner status is an exclusion criterion. Participants who meet the OHRP definition of a prisoner at any point during the follow-up phase of the study will be withdrawn from further participation.

Inclusion/Exclusion Checklist: This form will include each inclusion and exclusion criterion to document eligibility. It will gather data from the study screening visit as well as OTP record review prior to enrollment. The record review will include looking for evidence for meeting study eligibility (e.g. receiving specified number of methadone take-home doses, and being treated within the specified methadone dose range). Eligibility will be

assessed continually, as appropriate. Only participants who continue to meet study eligibility criteria will be allowed to continue with the screening process and study intervention.

Locator Form: A locator form is used to obtain information to assist in finding participants during treatment and at follow-up. The information on this form will also be used to contact participants to remind them of upcoming study visits. This form collects current address, email address, and phone numbers of the participant AND one or more family members/significant other, or friends. In order to facilitate locating participants if direct contact efforts are unsuccessful, addresses, email addresses and phone numbers of at least one other person (e.g., family members, significant others, friends) who may know how to reach the participant will be collected. This information will be collected at screening, and will be updated at each visit (as needed). No information from this form is used in data analyses nor is this information captured in the data capture system (RedCAP).

Demographics: Demographics form will collect information about demographic characteristics of the participant, including sex, date of birth, ethnicity, race, education, employment pattern, insurance status, and marital status.

Medical History and Charlson Comorbidity Index forms: Medical History form and Charlson Comorbidity Index form will obtain a medical and psychiatric history from the participant covering past and present health conditions to help determine eligibility and to provide baseline information (Austin et al., 2015). These data will be collected during screening only.

Psychosocial Counseling Attendance Form: Participants' psychosocial counseling attendance will be assessed at each visit (Intake/Baseline Visit and follow-up visits 2 through 4, or the Early Termination Visit if participant discontinues study participation early). It serves the purpose of monitoring and reporting whether counseling attendance matches what is recommended in the treatment plan at each visit. This will be accomplished through the data from the OTP records.

Concomitant Medications: Concomitant medications will be collected on the Concomitant Medications form at the Intake/Baseline Visit (Visit 1). Concomitant medications will be reviewed at every subsequent study visits (including Visit 4, or the Early Termination Visit if the participant discontinues study participation early), and changes will be documented on the form. The study medical clinician may exclude any participant taking medications that could interact adversely with methadone at his/her clinical discretion.

Study Completion: This form tracks the participant's status in the study. It will be completed at the last research visit (for participants who complete the study) or at the Early Termination Visit (for participants who discontinue study participation early). For participants who do not complete a final visit, the Study Completion form will be completed once the Visit 4 research visit window elapses. This form will be used in data analyses to address variables such as treatment retention and completion.

Protocol Deviations: Protocol Deviations will be assessed and documented throughout the study. This form will document a description of the deviation, how it occurred, the corrective action taken to resolve the specific deviation, as well as a description of the plan implemented to prevent future occurrences of similar deviations.

Missed Study Assessment Visit: This form is designed to capture the reason a study visit was missed. Once the visit window closes without completion of the visit, this assessment will be completed directly in the electronic data capture system. Completing this form will remove the requirement for all assessments scheduled for that visit. Active tracking and follow-up should be performed for all missed visits.

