4.4.2. Safety Assessments

Patient Health Questionnaire (PHQ-9): The PHQ-9 (Spitzer et al., 1999) is a validated, self-administered version of the PRIME-MD, contains the mood (PHQ-9) module as covered in the original PRIME-MD. It will be administered at Intake/Baseline and repeated at each follow-up visit and the Early Termination Visit if participant discontinues study participation early. Endorsements of suicidality on the PHQ-9 (i.e., if the participant answers Q9 ("Thoughts that you would be better off dead, or of hurting yourself in some way") as

“Several days”, “More than half the days” or “Nearly every day”) will trigger the completion of the P4 Screener form and an immediate report to the study’s physician and PI.

P4 Screener for suicide risk: The P4 Screener (Dube et al., 2010) is a brief measure (approximately 5 minutes) used for assessing potential suicide risk in primary care. The participant will answer 4 questions regarding past attempts, a plan, probability of completing suicide, and preventive factors at screening to exclude active suicidal ideation at Intake/Baseline. If the participant answers “Yes” to Question 2 of P4 Screener, “Have you thought about how you might actually hurt yourself?”, research staff will ask the participant additional clarifying questions to assess suicidality (Suicidal Risk form). A safety standard operating procedure will be indicated in the Manual of Operating Procedures (MOP), including the decision tree, assessment processes and documentation, and procedures to contact the study physician, study pharmacist, and the designated on-site crisis responder for assessment of the participant’s intent to harm and disposition.

Pregnancy and Birth Control Assessment: This form will document childbearing potential, and female participants' self-reported pregnancy status and use of an acceptable method of birth control. The Pregnancy and Birth Control Assessment will be collected during screening (Visit 1) to determine eligibility. For females of childbearing potential: Self-reported contraceptive use and pregnancy status will be performed at Visit 1 to confirm participant eligibility. Birth Control assessment and self-reported pregnancy question will also be administered at Visits 2 through 4. Pregnancy occurring during the study will be reported to Site PI for additional clinical monitoring, referral to pre-natal care (as needed), and the participant will be withdrawn from the study.

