satisfaction with treatment will be recorded on the Treatment Satisfaction Survey (based on a 5-point Likert scale: 0 = very dissatisfied, to 5 = very satisfied) that is completed by study participants at each study visit (1-4), including the Early Termination Visit (if participant discontinues study participation early). Pharmacists and physicians will also be asked to complete the Treatment Satisfaction Survey once per month, beginning the month of the first participant, first visit (FPFV; Visit 1) at their paired site and ending the month of the last participant, last visit (LPLV) at their paired site.

End of Methadone Medication Form: This form tracks the participant's status with regard to the study intervention/medication. It will be completed at the pharmacy at the Early Termination Visit (if participant discontinues study participation early), or at the LAST visit at the pharmacy for methadone administration and dispensing, which will occur about 3 months after the first pharmacy visit. Remote/virtual interviews by phone or the Duke-approved teleconferencing platform for research may be used to collect study assessments for participants who discontinue study participation early and are unable to return for Early Termination Visit during the specified time period.

Methadone Treatment Education Feedback Questionnaire: We will collect the opinions of pharmacists and OTP physicians about the clarity and utility of the study training materials, as well as any lack of useful information from the training. The questionnaire will consist of specific questions on the training modules to be rated on a 5-point Likert Scale of satisfaction, and will be filled out at the end of the training phase and once all participants have completed the study. The results will be used to structure training materials for a subsequent clinical trial.

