- ✚ Data on fatal overdoses may be collected via medical chart record review, if medical records data is available, at Visit 4 (or the Early Termination Visit if the participant discontinues study participation early). This will be supplemented with information from contacts with persons listed on the participant's locator form when participants are lost to follow-up throughout the study. Fatal overdoses will be captured on the Safety Event Response Checklist.
- ✚ All deaths, regardless of cause, will be captured for this study. These events will be identified through the participants' locator information, or when possible through using state medical examiner records, National Death Index, and/or review of medical records. Deaths will be reported using the Safety Event Response Checklist.

(3.) Urine drug screens (UDS) will be collected by the OTP clinic at Intake/Baseline, at each monthly research visit (1 month, 2 months, and 3 months following study intake), and/or as needed based on clinical decision.

- ✚ In this study, UDS results demonstrating ongoing opioid use or other illicit/nonmedical substance use (e.g., cocaine) will be reported to the site PI to determine whether the participant should continue in the study.
- ✚ If illicit or non-prescribed opioid use is reported, found on drug testing, or suspected at any time during treatment, the participant will be contacted to perform at least one random UDS (as needed) prior to the next scheduled visit and referred to the study physician for an assessment and to determine whether the participant should continue in the study.
- ✚ Any non-prescribed use of benzodiazepines that is detected will prompt analogue measures to those adopted for opioid use. The abuse of other substances or alcohol will result in early termination from the study and return to the OTP for methadone dosing and possible adjustment of the take home schedule.

(4.) Measures of adherence will be monitored and assessed, including: (1) adherence to scheduled pharmacy visits for dose administration and take-home pickup and (2) success in methadone call-back (e.g., failed methadone dose call back as an indicator treatment non-adherence). Failure to attend the random methadone dose call-back visit will be considered as an indicator of non-adherence.

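### Several text passages number the visits as if there were four, so Visit 4 reads as the last visit, whereas in Table 1 Visit 4 is month 2 and the last visit is Visit 5 at month 3

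*Combined protocol and SAP*

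**What the plan says.** Table 1 (Section 4.4) defines five visits. Visit 1 is screening and baseline, and Visit 2 is the first methadone dosing at the pharmacy. Visit 3 follows one month later, Visit 4 is headed "2 Months After Visit 2" and Visit 5 is headed "3 Months After Visit 2". A note under the table adds: "The timing of the subsequent follow-up visits are anchored at visit 2". The Study Completion form is marked only at Visit 5 and Early Termination.

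Section 4.4.1 opens by tying itself to that table: "The visit numbers used in this section follow the order indicated in the Study Assessment Timetable". Its Study Completion paragraph then says that, for participants who do not complete a final visit, "the Study Completion form will be completed once the Visit 4 research visit window elapses". It also says that the form supplies the retention and completion variables for analysis.

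The same pattern appears elsewhere:

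- Section 15.2, item (2), allows a chart review for fatal overdose "at Visit 4 (or the Early Termination Visit if the participant discontinues study participation early").
- Section 4.4.2 says: "Birth Control assessment and self-reported pregnancy question will also be administered at Visits 2 through 4".
- Section 4.4.4 has the satisfaction survey "completed by study participants at each study visit (1-4").
- Section 4.4.1 gives follow-up visits 2 to 4 for counselling attendance, and names Visit 4 among the later visits at which concomitant medication is reviewed.

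**The concern.** The passages on Study Completion, fatal-overdose review and the pregnancy check are instructions to staff, and forms and visit schedules may be built from them. Read with the only visit numbering that the protocol defines, they act at month 2 of a three-month follow-up.

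Three things are at stake. A participant without a final visit could have a completion status recorded before the third month has run, although Section 2, objective (c), concerns retention over the whole three months. A chart review done at month 2 cannot show a fatal overdose in the third month of pharmacy dispensing. And the text on the pregnancy check omits the month-3 visit that Table 1 schedules, while adding Visit 2, for which Table 1 schedules no such check. Under Section 4.4.2 a pregnancy leads to withdrawal, so text and table need to agree on when the question is asked.

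**Working it through.** No sample size, power or error rate is involved. The check maps each visit number in the text to Table 1 and compares it with the visits that Table 1 marks.

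**Step 1. The two numberings.**

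| Event | Table 1 | Numbering that the text appears to use |
|---|---|---|
| Baseline | Visit 1 | Visit 1 |
| First pharmacy dose | Visit 2 | not numbered |
| Month 1 | Visit 3 | Visit 2 |
| Month 2 | Visit 4 | Visit 3 |
| Month 3 (last) | Visit 5 | Visit 4 |

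Every disputed reference makes sense in the right-hand column, which suggests text left from a scheme that did not count the pharmacy visit. That is an inference; the protocol does not describe such a scheme.

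**Step 2. Each reference against Table 1.**

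| Item | Text | Table 1 | Does other wording in the text cover month 3? |
|---|---|---|---|
| Study Completion, no final visit (4.4.1) | after Visit 4 window | Visit 5 or Early Termination | Partly: for completers the form is done at the last research visit |
| Fatal-overdose chart review (15.2) | Visit 4 or Early Termination | no separate row | Partly: 4.4.2 describes the review without a visit number |
| Pregnancy and birth control (4.4.2) | Visits 2 to 4 | follow-up Visits 3, 4, 5 | No |
| Counselling attendance (4.4.1) | follow-up visits 2 to 4 | follow-up Visits 3, 4, 5 | Yes: assessed at each visit |
| Concomitant medication (4.4.1) | later visits, Visit 4 included | follow-up Visits 3, 4, 5 | Yes: every later visit |
| Satisfaction (4.4.4) | Visits 1 to 4 | Visits 1, 3, 4, 5 | Yes: each visit, also in Section 2(f) and Section 13.2 |

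**Step 3. Size of the gap.** Visit 5 minus Visit 4 is 3 − 2 = 1 month. As a share of follow-up this is 1/3, about 33%. It is a nominal figure, because the protocol gives no window widths. For the pregnancy check, Visits 2 to 4 share two visits (3 and 4) with Table 1's Visits 3 to 5; the text adds Visit 2 and drops Visit 5.

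**Step 4. Who is reached.** The close-out sentence covers only participants without a final visit. Their number is unknown. If all 20 places are filled, one participant is 1/20 = 5 percentage points of a proportion of participants, so even one wrongly recorded status would be visible.

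**The case against.** The strongest reply is that this is a numbering slip which staff would see through, and that the protocol secures the third month elsewhere. Much of that stands.

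- The close-out sentence depends on the final visit having been missed. That cannot be known until the month-3 window has closed, so a month-2 close-out defeats the sentence's own condition. Completers and those with an Early Termination Visit are unaffected.
- Retention is defined apart from the form date: over the three-month phase in Section 2(c), and over three follow-up assessments in Section 13.2. The End of Methadone Medication Form also tracks treatment status to about three months.
- The chart review is permissive. Sections 4.4.2 and 15.2 also provide for locator contacts and, when possible, medical examiner records, the National Death Index and medical records. A reader might infer that a fatal overdose in month 3 would be missed; the documents do not support that.
- A reader might also infer that the text drops the whole month-3 assessment for everyone. It does not. Sections 4.3, 5 and 13.2 require that assessment, and the PHQ-9, TLFB, urine screen and safety checklist are set for each follow-up or monthly visit.
- The numbering statement formally covers Section 4.4.1 only. In Sections 4.4.2, 4.4.4 and 15.2, Visit 4 could mean the fourth research visit.

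The reply does not remove the contradiction. Section 4.4.1 excludes a separate numbering in its own words, and Table 1 is the only numbering defined for the other sections. The pregnancy check has no wording about every visit to fall back on.

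**Conclusion.** The inconsistency is real. By Table 1, three instructions are wrong as written: the Study Completion close-out for participants without a final visit, the visit named for the optional fatal-overdose chart review, and the visits listed for the pregnancy and birth-control check. The numbers for counselling, concomitant medication and satisfaction are mislabelled, but those assessments are not cut short.

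The nominal gap is one month of three. Its effect on completion status is confined to participants without a final visit, and other routes for detecting deaths remain. In a descriptive pilot with no hypothesis test I rate this minor to moderate. The documents do not support treating it as a general loss of month-3 data or as a failure to ascertain deaths.

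This rests on Table 1 being the intended schedule, as the three-month follow-up in Sections 2(c), 5 and 13.2 suggests. Months are counted from Visit 2, as in Table 1 and Section 5. Section 4.3 counts them from baseline, but that does not change which visit number is last.

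**What to change.** Reconcile Sections 4.4.1, 4.4.2, 4.4.4 and 15.2 with Table 1. The safer way is to name visits by month. If numbers are kept:

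- the final visit is Visit 5;
- the monthly follow-up visits are Visits 3 to 5 (counselling attendance, concomitant medication, and the pregnancy and birth-control check as Table 1 marks it);
- the participant satisfaction survey is at Visits 1, 3, 4 and 5.

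For participants without a final visit, complete the Study Completion form after the Visit 5 window closes, and do the fatal-overdose record review at or after that point. State the window widths, so that the closing date can be determined. Then check that the form schedule in the data capture system matches.

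The cost is a wording amendment, which Section 15.3 requires the IRB to approve before use, and one check of the form schedule. No participants or procedures are added beyond what Table 1 already contains.
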